6.4. Dose Modification and Toxicity Management

The following general guidance should be followed for management of toxicities.

- Treat each of the toxicities with maximum supportive care (including holding the agent suspected of causing the toxicity if required).
- If the symptoms promptly resolve with supportive care, consideration should be given to continuing the same dose of the assigned IP along with appropriate continuing supportive care. If medically appropriate, dose modifications are permitted
- All dose modifications should be documented with clear reasoning and documentation of the approach taken.

6.4.1. Durvalumab + tremelimumab

Dose reductions are not permitted. In case of doubt, the Investigator should consult with the Study Physician.

Guidelines for the management of immune-mediated reactions, infusion-related reactions, and non-immune-mediated reactions for durvalumab monotherapy and durvalumab + tremelimumab are provided in the Dosing Modification and Toxicity Management Guidelines in Appendix 1.Error!

Reference source not found.

In addition, there are certain circumstances in which durvalumab and/or tremelimumab should be permanently discontinued.

Following the first dose of durvalumab +/- tremelimumab, subsequent administration of durvalumab +/- tremelimumab can be modified based on toxicities observed (see Appendix 1).

Based on the mechanism of action of durvalumab or tremelimumab leading to T-cell activation and proliferation, there is the possibility of observing immune related Adverse Events (irAEs) during the conduct of this study. Potential irAEs include immune-mediated enterocolitis, dermatitis, hepatitis, and endocrinopathies. Subjects should be monitored for signs and symptoms of irAEs. In the absence of an alternate etiology (e.g., infection or PD) signs or symptoms of enterocolitis, dermatitis, hepatitis, and endocrinopathy should be considered to be immune-related.

In addition, management guidelines for adverse events of special interest (AESIs) are detailed in Section 9.1.3. All toxicities will be graded according to NCI CTCAE v4.0

7. Restrictions During the Study and Concomitant Treatment(s)

The following restrictions apply while the patient is receiving study treatment and for the specified times before and after:

Female patient of child-bearing potential

Females of childbearing potential who are sexually active with a non-sterilized male partner must use at least 1 **highly** effective method of contraception (Table 3) from the time of screening and must

18 November 2020 Page **79** of **164**

agree to continue using such precautions for 180 days after the last dose of durvalumab + any drug combination therapy or 90 days after the last dose of durvalumab monotherapy. Non-sterilized male partners of a female patient must use male condom plus spermicide throughout this period. Cessation of birth control after this point should be discussed with a responsible physician. Not engaging in sexual activity for the total duration of the drug treatment and the drug washout period is an acceptable practice; however, periodic abstinence, the rhythm method, and the withdrawal method are not acceptable methods of birth control. Female subjects should also refrain from breastfeeding throughout this period.

Male subjects with a female partner of childbearing potential

- Non-sterilized males who are sexually active with a female partner of childbearing potential
 must use a male condom plus spermicide from screening through 180 days after receipt of
 the final dose of durvalumab + any drug combination therapy or 90 days after receipt of the
 final dose of durvalumab monotherapy. Not engaging in sexual activity is an acceptable
 practice; however, occasional abstinence, the rhythm method, and the withdrawal method
 are not acceptable methods of contraception. Male subjects should refrain from sperm
 donation throughout this period.
- Female partners (of childbearing potential) of male subjects must also use a highly effective method of contraception throughout this period (Table 3).

Females of childbearing potential are defined as those who are not surgically sterile (ie, bilateral tubal ligation, bilateral oophorectomy, or complete hysterectomy) or post-menopausal.

Women will be considered post-menopausal if they have been amenorrheic for 12 months without an alternative medical cause. The following age-specific requirements apply:

- Women <50 years of age would be considered post-menopausal if they have been amenorrheic for 12 months or more following cessation of exogenous hormonal treatments and if they have luteinizing hormone and follicle-stimulating hormone levels in the postmenopausal range for the institution or underwent surgical sterilization (bilateral oophorectomy or hysterectomy).
- Women ≥50 years of age would be considered post-menopausal if they have been amenorrheic for 12 months or more following cessation of all exogenous hormonal treatments, had radiation-induced menopause with last menses >1 year ago, had chemotherapy-induced menopause with last menses >1 year ago, or underwent surgical sterilization (bilateral oophorectomy, bilateral salpingectomy or hysterectomy).

Highly effective methods of contraception, defined as one that results in a low failure rate (ie, less than 1% per year) when used consistently and correctly are described in Table 3. Note that some contraception methods are not considered highly effective (e.g., male or female condom with or without spermicide; female cap, diaphragm, or sponge with or without spermicide; non-copper containing intrauterine device; progestogen-only oral hormonal contraceptive pills where inhibition

18 November 2020 Page **80** of **164**

of ovulation is not the primary mode of action [excluding Cerazette/desogestrel which is considered highly effective]; and triphasic combined oral contraceptive pills).

TABLE 3. HIGHLY EFFECTIVE METHODS OF CONTRACEPTION (<1% FAILURE RATE)

Barrier/Intrauterine methods	Hormonal Methods
Copper T intrauterine device	Etonogestrel implants: eg Implanon or Norplant
Levonorgestrel-releasing intrauterine system (eg, Mirena®) ^a	Intravaginal device: eg ethinylestradiol and etonogestrel
(eg, Milleria)	etonogestrei
	Medroxyprogesterone injection: eg Depo- Provera
	Normal and low dose combined oral contraceptive pill
	Norelgestromin/ethinylestradiol transdermal system
	Cerazette (desogestrel)

^a This is also considered a hormonal method

Blood donation

Subjects should not donate blood while participating in this study.

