4.4. Permanent Discontinuation of Study Therapy

An individual subject will not receive any further investigational product if any of the following occur in the subject in question:

Withdrawal of consent or lost to follow-up

Adverse event that, in the opinion of the investigator or the sponsor, contraindicates further dosing

Subject is determined to have met one or more of the exclusion criteria for study participation at study entry and continuing investigational therapy might constitute a safety risk

Pregnancy or intent to become pregnant

Any AE that meets criteria for discontinuation as defined in Section 9.3.

- Serious Adverse event related to thoracic radiation, with the exception of toxicities that do not meet the criteria for discontinuation as defined in Section 9.3.
- Dose-limiting toxicity (See Section 6.3 for definition of DLT).
- Grade ≥ 3 infusion reaction

18 Nov 2020 Page **64** of **164**

- Subject noncompliance that, in the opinion of the investigator or sponsor, warrants withdrawal; e.g., refusal to adhere to scheduled visits
- Initiation of alternative anticancer therapy including another investigational agent
- Confirmation of PD and investigator determination that the subject is no longer benefiting from treatment with durvalumab
 + tremelimumab

Subjects who are permanently discontinued from further receipt of investigational product, regardless of the reason (withdrawal of consent, due to an AE, other), will be identified as having permanently discontinued treatment.

Subjects who are permanently discontinued from receiving investigational product will be followed for safety per Section 9.0 and Appendix 2 or 3, including the collection of any protocol-specified blood specimens, unless consent is withdrawn or the subject is lost to follow-up or enrolled I another clinical study. All subjects will be followed for survival. Subjects who decline to return to the site for evaluations will be offered follow-up by phone every 3 months as an alternative.

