6.3. Definition of Dose Limiting Toxicity (DLT)

Dose-limiting toxicities (DLTs) will be evaluated from the first day of administration of durvalumab (cohort 1) or durvalumab+tremelimumab (cohort 2), in this trial. The period for evaluating DLTs will be from the day of first administration of study therapy until 30 days after surgical resection or 100 days following the last dose of study therapy, whichever occurs later. Subjects who do not remain on the study up to this time for reasons other than DLT will be replaced with another subject. Grading of DLTs will follow the guidelines provided in the Common Terminology Criteria for Adverse Events (CTCAE) version 4.0. A patient who experiences a DLT will be permanently discontinued from treatment and will proceed to surgery after standard preoperative evaluation by a surgeon and anesthesiologist. Prior to surgery any treatment related toxicity should have resolved to ≤grade 1. [5]

A DLT will be defined as any Grade 3 or higher toxicity that occurs during the DLT evaluation period. Toxicity that is clearly and directly related to the primary disease or to another etiology is excluded from this definition. The following will be DLTs:

- Any Grade 4 irAE
- Any ≥ Grade 3 colitis
- Any Grade 3 or 4 non-infectious pneumonitis irrespective of duration
- Any Grade 2 pneumonitis that does not resolve to ≤ Grade 1 within 3 days of the initiation of maximal supportive care
- Any Grade 3 irAE, excluding colitis or pneumonitis, that does not downgrade to Grade 2 within 3
 days after onset of the event despite optimal medical management including systemic
 corticosteroids or does not downgrade to ≤ Grade 1 or baseline within 14 days
- Liver transaminase elevation > 8 × ULN or total bilirubin > 5 × ULN
- Any ≥ Grade 3 non-irAE, except for the exclusions listed below

The definition excludes the following conditions:

- Grade 3 fatigue lasting ≤ 7 days
- Grade 3 endocrine disorder (thyroid, pituitary, and/or adrenal insufficiency) that is managed
 with or without systemic corticosteroid therapy and/or hormone replacement therapy and the
 subject is asymptomatic
- Grade 3 inflammatory reaction attributed to a local antitumor response (e.g., inflammatory reaction at sites of metastatic disease, lymph nodes, etc.)
- Concurrent vitiligo or alopecia of any AE grade
- Grade 3 infusion-related reaction (first occurrence and in the absence of steroid prophylaxis) that resolves within 6 hours with appropriate clinical management

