Note: For asymptomatic amylase or lipase levels of >2.0×ULN, hold study drug/study regimen, and if complete work up shows no evidence of pancreatitis, study drug/study regimen may be continued or resumed.

Note: Study drug/study regimen should be permanently discontinued in Grade 3 events with high likelihood for morbidity and/or mortality – e.g., myocarditis, or other similar events even if they are not currently noted in the guidelines. Similarly, consider whether study drug/study regimen should be permanently discontinued in Grade 2 events with high likelihood for morbidity and/or mortality – e.g., myocarditis, or other similar events even if they are not currently noted in the guidelines – when they do not rapidly improve to Grade <1 upon treatment with systemic steroids and following full taper

Note: There are some exceptions to permanent discontinuation of study drug for Grade 4 events (i.e., hyperthyroidism, hypothyroidism, Type 1 diabetes mellitus).

Toxicity Management

- when these events are not responding to systemic steroids
- With long-term steroid and other immunosuppressive use, consider need for Pneumocystis jirovecii pneumonia (PJP, formerly known as Pneumocystis carinii pneumonia) prophylaxis, gastrointestinal protection, and glucose monitoring.
- Discontinuation of study drug/study regimen is not mandated for Grade 3/Grade 4 inflammatory reactions attributed to local tumor response (e.g., inflammatory reaction at sites of metastatic disease and lymph nodes). Continuation of study drug/study regimen in this situation should be based upon a benefit-risk analysis for that patient.

AE Adverse event; CTC Common Toxicity Criteria; CTCAE Common Terminology Criteria for Adverse Events; imAE immune-mediated adverse event; IV intravenous; NCI National Cancer Institute; PO By mouth.

Pediatric Considerations regarding Immune-Mediated Reactions

The criteria for permanent discontinuation of study drug/study regimen based on CTC grade/severity is the same for pediatric patients as it is for adult patients, as well as to permanently discontinue study drug/study regimen if unable to reduce corticosteroid ≤ a dose equivalent to that required for corticosteroid replacement therapy within 12 weeks of the start of the immunemediated event

Dose Modifications

Toxicity Management

- All recommendations for specialist consultation should occur with a pediatric specialist in the specialty recommended.

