- Once patients on steroids are improving, gradually taper immunosuppressive steroids (as appropriate and with guidance of endocrinologist) over ≥28 days and consider prophylactic antibiotics, antifungals, and anti-PJP treatment (refer to current NCCN guidelines for treatment of cancer-related infections).^a
- For patients with normal endocrine workup (laboratory assessment or MRI scans), repeat laboratory

18-Nov-2020 Page **143** of **164**

assessments/MRI as clinically indicated.

Grade 3 or 4

For Grade 3 or 4
endocrinopathy other than
hypothyroidism and Type
1 diabetes mellitus, hold
study drug/study regimen
dose until endocrinopathy
symptom(s) are controlled.
Study drug/study regimen
can be resumed once event
stabilizes and after
completion of steroid
taper.

Patients with
endocrinopathies who may
require prolonged or
continued steroid
replacement (e.g., adrenal
insufficiency) can be
retreated with study
drug/study regimen on the
following conditions:

- 1. The event stabilizes and is controlled.
- 2. The patient is clinically stable as per investigator or treating physician's clinical judgement.
- 3. Doses of prednisone are ≤10 mg/day or equivalent.

For Grade 3 or 4:

- Consult endocrinologist to guide evaluation of endocrine function and, as indicated by suspected endocrinopathy and as clinically indicated, consider pituitary scan. Hospitalization recommended.
- For all patients with abnormal endocrine work up, except those with isolated hypothyroidism or Type 1 DM, and as guided by an endocrinologist, promptly initiate empiric IV methylprednisolone 1 to 2 mg/kg/day or equivalent, as well as relevant hormone replacement (e.g., hydrocortisone, sex hormones).
- For adrenal crisis, severe dehydration, hypotension, or shock, immediately initiate IV corticosteroids with mineralocorticoid activity.
- Isolated hypothyroidism may be treated with replacement therapy, without study drug/study regimen interruption, and without corticosteroids.
- Isolated Type 1 diabetes mellitus may be treated with appropriate diabetic therapy and without corticosteroids. Only hold study drug/study regimen in setting of hyperglycemia when diagnostic workup is positive for diabetic ketoacidosis.

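### Appendix 1 lets study drug resume after events that Sections 4.4 and 6.3 make permanent-stop DLTs, and Section 6.4.1 does not say which text governs

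*Combined protocol and SAP*

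**What the plan says.** Section 6.3 defines the DLTs and their consequence: "A patient who experiences a DLT will be permanently discontinued from treatment". Section 4.4 lists the events after which a subject receives no more investigational product, and includes "Dose-limiting toxicity (See Section 6.3 for definition of DLT"). Neither section allows an exception once an event qualifies.

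Section 6.4.1 deals with dosing after toxicity. It forbids dose reductions, sends the investigator to Appendix 1 for management guidelines, and says that after the first dose "subsequent administration of durvalumab +/- tremelimumab can be modified based on toxicities observed (see Appendix 1"). On permanent stops it says only that "there are certain circumstances in which durvalumab and/or tremelimumab should be permanently discontinued", without naming those circumstances or citing Section 4.4 or 6.3. It refers doubtful cases to the Study Physician. Section 6.4 favours considering the same dose again when symptoms settle promptly.

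Appendix 1 sets hold, resume and stop rules by event and grade. Its endocrinopathy row for Grade 3 or 4 says that drug "can be resumed once event" stabilizes and the steroid taper is complete. Its general notes add: "There are some exceptions to permanent discontinuation of study drug for Grade 4 events (i.e., hyperthyroidism, hypothyroidism, Type 1 diabetes mellitus").

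**The concern.** One event can lead to opposite dosing decisions depending on the section consulted. Most of the rows at issue permit what Section 6.3 forbids. The Grade 3 non-immune row goes further and directs resumption, so both texts cannot be followed.

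What is at stake is re-exposure to a checkpoint inhibitor after a protocol-defined DLT, shortly before lung resection, in a trial whose primary endpoints are safety and feasibility. Section 1.11 singles out pulmonary toxicity for attention in this setting, and the Grade 2 pneumonitis row is among those that conflict.

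**Working it through.** The plan states no figure to reproduce. The check sets each Appendix 1 row against the Section 6.3 list and exclusions, then asks whether the schedule leaves room for a further dose.

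**Rows side by side**

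| Appendix 1 row | What Appendix 1 allows | Section 6.3 | Where they conflict |
|---|---|---|---|
| Endocrinopathy, Grade 4 | Hold until controlled, then resume; isolated hypothyroidism needs no interruption; isolated type 1 diabetes is held only for ketoacidosis | "Any Grade 4 irAE" is a DLT; the endocrine exclusion covers asymptomatic Grade 3 only | At Grade 4 |
| Colitis, Grade 3 | Resume after taper if Grade ≤1 within 14 days; patients on CTLA-4 inhibitors stop | "Any ≥ Grade 3 colitis", with no duration condition | Cohort 1 only |
| Pneumonitis, Grade 2 | Restart at the physician's judgment after recovery and taper; no recovery limit in the row | DLT unless Grade ≤1 within 3 days of maximal supportive care | Recovery after 3 days |
| Peripheral neuromotor, Grade 3 | Hold until Grade ≤1; stop if unresolved at 30 days or with respiratory or autonomic signs | DLT unless Grade 2 within 3 days and Grade ≤1 or baseline within 14 days | Events that miss either limit but resolve by day 30 |
| Myositis, Grade 3 | Same, with respiratory signs only | Same | Same |
| Rash, Grade 3 | Resume after recovery and taper; no time limit in the row | Same | Events that miss either limit |
| Transaminases >5 to 8×ULN | Resume after taper if ≤3×ULN within 14 days (normal baseline) | Below the >8×ULN line, but subject to the same 3-day and 14-day limits if graded 3 (assumed; the row prints no grade) | Mainly the 3-day limit |
| Non-immune, treatment-related, Grade 3 | Directs resumption if Grade ≤2 within 7 days or Grade ≤1 or baseline within 14 days | Every Grade 3 or higher non-immune event outside the exclusions is a DLT | Any such event not excluded |

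That is eight rows, and it is a minimum. The Grade 4 amylase/lipase and Grade 4 non-immune laboratory entries also leave continuation to judgment.

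**Details of the limits**

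- For neuromotor syndromes and myositis it is tempting to set 30 days against 14 and conclude that only events resolving on days 15 to 30 conflict. Section 6.3 also has a 3-day limit. An event still at Grade 3 on day 4 is already a DLT, even if it resolves on day 10. These two rows print no resume instruction; resumption follows from holding only until resolution.
- In the Grade 2 pneumonitis row, escalation to infliximab takes (3 to 5) + (2 to 3) = 5 to 8 days, and restart remains open afterwards. Two general limits apply: the 12-week limit for reducing steroids, and a note to consider stopping for high-risk Grade 2 events that do not improve rapidly. The second is a prompt to consider and does not name pneumonitis.

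**Room in the schedule**

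Inputs: doses on days 1, 30 and 60 (Section 6.2.1); dose 2 must fall within radiation and dose 3 before planned surgery (Section 3.1.5); surgery up to 8 weeks after radiation; tapers of at least 28 days in most of these rows. Let T be the last day of radiation.

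- After dose 1, days available for onset plus improvement if dose 2 is still to be given: T − 28 − 1.
- After dose 2 on day 30, the same for dose 3: (T + 56) − 28 − 30.

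| T | Basis | Before dose 2 | Before dose 3 |
|---|---|---|---|
| 28 | Latest day in Section 6.2.1 | −1 (not possible) | 26 |
| 33 | Assumed: 25 fractions, 5 per week, starting on a Monday | 4 | 31 |
| 47 | 33 + 14, reading the ±2 in Section 3.1.4 as weeks | 18 | 45 |

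The last column is an upper bound, because it puts dose 3 at the very end of the surgical window. After a steroid-treated event dose 2 is mostly out of reach, but dose 3 is not. The non-immune row, isolated hypothyroidism and isolated type 1 diabetes require no taper, so these limits do not bind there.

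**The case against.** The strongest reply is that precedence can be inferred. Section 4.4 is categorical, while Section 9.1.3 describes Appendix 1 as an aid to the investigator's clinical judgment. Section 6.4.1 itself says that some circumstances call for a permanent stop, and it sends doubts to the Study Physician. An investigator who reads the whole protocol will stop.

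That is a sensible reading, but no text states it. Section 6.4.1 names Appendix 1 as its dosing reference, and the non-immune row is worded as a direction. The Study Physician line helps only someone who notices the conflict; a reader of the appendix row alone sees a clear answer.

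A second reply is that Appendix 1 carries general safeguards. Its notes call for a permanent stop after Grade 3 events with a high likelihood of morbidity or mortality, even where not listed, and this could reach severe neuromotor syndromes. That softens the neuromotor row, although the specific row still says to hold. It does not touch the Grade 4 endocrine, colitis or non-immune rows.

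A third reply is that three doses and long tapers leave little room to resume. This stands in part: the window is narrow for steroid-treated events, and events after dose 3 have no dosing consequence.

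A reader might infer that Section 6.4.1 tells investigators to follow Appendix 1 alone, or that the plan authorizes re-dosing after DLTs generally. The documents support neither. The wording is permissive, it acknowledges other stopping circumstances, and Sections 4.4 and 6.3 remain in force.

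**Conclusion.** The concern holds as a contradiction between stated rules with no order of precedence. At least eight Appendix 1 rows permit or direct dosing after events that are, or can be, DLTs. Four of them (neuromotor, myositis, rash, transaminases) conflict only when the event misses the 3-day or 14-day limit; colitis conflicts in cohort 1 only; the transaminase row depends on the range being Grade 3.

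The number of patients affected cannot be derived. Section 1.11 gives overall toxicity and pneumonitis rates, but not the share that is Grade 2 and slow to resolve, and the documents give no usable rate for the other rows.

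A reader might also infer that the stopping boundaries are compromised. They are not. Whether an event is a DLT is settled by Section 6.3, whatever dosing follows, so DLT counts, stopping rules and sample size stand. This is a patient-safety clarification worth making, not a flaw in the statistical design.

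**What to change.** Add one sentence to Section 6.4.1: *Any event that meets the Section 6.3 DLT definition or a Section 4.4 criterion requires permanent discontinuation, whatever Appendix 1 permits or directs, including its Grade 4 exceptions.*

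This resolves every row above, and any not listed, without editing the sponsor-prepared appendix. The cost is one sentence at the next amendment, with the IRB approval that Section 13.4 requires. It adds no procedures, visits or patients. If the investigators do want some of these events to be re-dosable, for example Grade 4 hypothyroidism on replacement therapy, the alternative is to amend Sections 4.4 and 6.3 explicitly. That would need a review of the safety monitoring, because it could change what counts as a DLT.

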3.1.5. Toxicity assessments

Safety will be monitored continuously by the study investigators for patients in both cohort 1 and cohort 2 through day 90 following the last dose of study therapy or 30 days after the day of surgery, whichever happens later. Details of safety assessments as detailed in

section 9.0 of this protocol. A detailed statistical analysis plan for safety and feasibility is contained in section 11 of this protocol.

Dose Delays due to Toxicity:

If patients, after receiving the first dose of study therapy (Day 1) are unable to receive the second dose on Day 30 (+/-3 days), therapy may be deferred as long as the second dose is received during the time period of thoracic radiation. If this is not possible, they will be discontinued from study therapy and will proceed to surgery after standard preoperative evaluation.

If patients, after receiving the second dose of study therapy (Day 30) are unable to receive the

third dose on Day 60 (+/-3 days), therapy may be deferred as long as the third dose is received during the pre-surgical window prior to planned surgery. If this is not possible, they will be discontinued from study therapy and will proceed to surgery after standard preoperative evaluation. Prior to surgery any treatment-related toxicity should have resolved to ≤grade 1. □

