3.2. Study Oversight for Safety Evaluation

Early trial termination will be the result of the criteria specified below:

Quality or quantity of data recording is inaccurate or incomplete.

Poor adherence to protocol and regulatory requirements.

Incidence or severity of adverse drug reaction in this or other studies indicates a potential health hazard to subjects.

Plans to modify or discontinue the development of the study drug.

In the event of an AstraZeneca decision to no longer supply study drug, ample notification will be provided so that appropriate adjustments to subject treatment can be made.

4. Patient Selection, Enrollment, Restrictions, Discontinuation and Withdrawal

Each patient must meet all of the inclusion criteria and none of the exclusion criteria for this study. Under no circumstances will there be exceptions to this rule.

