- 17. Current or prior use of immunosuppressive medication within 14 days before the first dose of durvalumab or tremelimumab. The following are exceptions to this criterion: Intranasal, inhaled, topical steroids, or local steroid injections (e.g., intra articular injection). Systemic corticosteroids at physiologic doses not to exceed 10 mg/day of prednisone or its equivalent, Steroids as premedication for hypersensitivity reactions (e.g., CT scan premedication).
- 18. Receipt of live attenuated vaccine within 30 days prior to the first dose of IP. Note: Subjects, if enrolled, should not receive live vaccine whilst receiving IP and up to 30 days after the last dose of IP.
- 19. Known allergy or hypersensitivity to any of the study drugs or any of the study drug excipients.
- 20. Prior randomisation or treatment in a previous durvalumab and/or tremelimumab clinical study regardless of treatment arm assignment.
- 21. Has history of (non-infectious) pneumonitis that required steroids, evidence of interstitial lung disease or active, non-infectious pneumonitis.
- 22. Prior history of thoracic irradiation for any indication.
- 23. Subjects who are only deemed suitable for surgical management of stage III NSCLC with pneumonectomy, as determined by an attending thoracic surgeon.
- 24. Any condition that, in the opinion of the investigator, would interfere with evaluation of study treatment or interpretation of patient safety or study results

18 Nov 2020 Page **63** of **164**

- 25. Female patients who are pregnant or breastfeeding or male or female patients of reproductive potential who are not willing to employ or employing an effective method of birth control from screening to 180 days after the last dose of durvalumab + tremelimumab combination therapy or 100 days after the last dose of durvalumab monotherapy, whichever is the longer time period
- 26. Uncontrolled psychiatric illness/social situations that would limit compliance with study requirements or compromise the ability of the subject to give written consent
- 27. Procedures for withdrawal of incorrectly enrolled patients are presented in Section 4.3. If a patient withdraws from participation in the study, then his or her enrollment code cannot be reused. Withdrawn patients will not be replaced.

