6.2. Dosage and Administration

6.2.1. Durvalumab monotherapy or Durvalumab and Tremelimumab

Dosage of study therapy to be administered in this protocol is outlined below in Table 2.

In cohort 1: Three doses of durvalumab monotherapy will be administered to enrolled patients on Days 1, 30 and 60 (+/- 3 days) concurrently with standard thoracic radiation from day 1 until days 25-28, prior to planned surgery. Thoracic surgery will take place 6-8 weeks after completion of thoracic radiation.

In cohort 2: Three doses of durvalumab + tremelimumab will be administered to enrolled patients on Days 1, 30 and 60 (+/- 3 days) concurrently with standard thoracic radiation from day 1 until day 25-28 prior to planned surgery. Thoracic surgery will take place 6-8 weeks after completion of thoracic radiation.

Dosing of study therapy is flat dosing.

TABLE 2: TRIAL TREATMENT

Drug	Dose/Potency*	Dose Frequency	Route of Administration	Regimen/Treatment Period	Use
Durvalumab	1500 mg	Q4W	IV infusion	Day 1 of each 4 week cycle	Experimental
Tremelimumab	75mg	Q4W	IV infusion	Day 1 of each 4 week cycle	Experimental
(cohort 2 only)					

18 Nov 2020 Page **73** of **164**

The rationale for dosing is outlined in sections 1.0 and 5.0. Trial treatment should begin on the day of registration or as close as possible to the date on which treatment is allocated/assigned. Refer to Section 5.0 for the administration and monitoring of administration of durvalumab and tremelimumab.

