9.3.12.3.2. Paternal Exposure

Male subjects should refrain from fathering a child or donating sperm during the study and for 180 days after the last dose of durvalumab +/- tremelimumab or 90 days after the last dose of durvalumab +/- tremelimumab, whichever is the longer time period.

18-Nov-2020 Page **110** of **164**

Pregnancy of the patient's partner is not considered to be an AE. However, the outcome of all pregnancies (spontaneous miscarriage, elective termination, ectopic pregnancy, normal birth, or congenital abnormality) occurring from the date of the first dose until 180 days after the last dose of durvalumab +/- tremelimumab or 90 days after the last dose of durvalumab +/- tremelimumab, whichever is the longer time period should, if possible, be followed up and documented.

Where a report of pregnancy is received, prior to obtaining information about the pregnancy, the Investigator must obtain the consent of the patient's partner. Therefore, the local study team should adopt the generic ICF template in line with local procedures and submit it to the relevant Ethics Committees (ECs)/Institutional Review Boards (IRBs) prior to use.

10. Disease Evaluation and Methods

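### Cohort 1 contraception: the period Section 7 requires stops 90 days after the last durvalumab dose, exclusion 25 asks for 100 days, and nothing says which governs

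*Combined protocol and SAP*

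**What the plan says.** Three places in the protocol set a period.

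- **Section 4.2, exclusion 25 (both sexes).** Patients of reproductive potential are excluded unless they use, or are willing to use, effective birth control from screening to 180 days after the combination or "100 days after the last dose of durvalumab monotherapy, whichever is the longer time period". The opening of Section 4 says of the entry criteria: "Under no circumstances will there be exceptions to this rule".
- **Section 7 (restrictions during the study).** Women must agree to continue contraception for 180 days after combination therapy or "90 days after the last dose of durvalumab monotherapy". The women's paragraph adds: "Cessation of birth control after this point should be discussed with a responsible physician". The men's paragraph has the same split, 180 days after "the final dose of durvalumab + any drug combination therapy or 90 days after receipt of the" last monotherapy dose. Partner contraception, breastfeeding and sperm donation are tied to the same period.
- **Section 9.3.12.3.2 (paternal exposure).** Men are to avoid fathering a child or donating sperm for "180 days after the last dose of durvalumab +/- tremelimumab or 90 days after the last dose of durvalumab +/- tremelimumab", whichever is longer. The sentence on following up partner pregnancies uses the same two periods and the same label on both.

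The synopsis version of the exclusion gives no duration.

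**The concern.** Exclusion 25 and Section 7 count from the same event, the last dose of durvalumab monotherapy, and give different end points. A cohort 1 patient who would accept 90 days but not 100 is ineligible. Once enrolled, the same patient is required by Section 7 to continue for only 90 days. A site that follows Section 7 to the letter would release a woman from a precaution she had to accept at entry.

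What is at stake is the clarity of a participant-protection instruction. Patients and sites need one end date, and the other restrictions that Section 7 ties to this period inherit the ambiguity.

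**Working it through.** The plan has no calculated figure to reproduce here, so the check sets the texts side by side.

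| Place | Applies to | After monotherapy | After combination |
|---|---|---|---|
| 4.2, exclusion 25 | women and men | 100 days by regimen; 180 if the closing clause is literal | 180 days |
| 7, women's paragraph | women | 90 days | 180 days |
| 7, men's paragraph | men | 90 days | 180 days |
| 9.3.12.3.2 | men; partner pregnancies | 180 days read literally; 90 if the labels are a slip | 180 days |

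**Cohort 2.** All rows give 180 days, so the conflict is confined to cohort 1.

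**Size of the gap between exclusion 25 and Section 7.** Let L be the day of the last dose.

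- By regimen: (L + 100) − (L + 90) = 10 days.
- Closing clause literal: (L + 180) − (L + 90) = 90 days.

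L cancels, so the gap does not depend on when dosing stops or on whether dose 3 is deferred under Section 3.1.5. With dose 3 on its scheduled day 60, Section 7 ends at day 60 + 90 = 150. Exclusion 25 ends at day 60 + 100 = 160 by regimen, or at day 60 + 180 = 240 read literally. No reading of exclusion 25 gives 90 days.

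**Is there a precedence rule?** The no-exceptions sentence in Section 4 concerns entry and does not rank Section 4.2 above Section 7. The longer-of clause in exclusion 25 chooses between that item's own two periods, not between sections. The advice to consult a physician appears only in the women's paragraph of Section 7 and adds no days. Section 9.3.12.3.2 carries the same drug label on both periods, so it cannot settle the monotherapy figure.

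**Women.** Only exclusion 25 and Section 7 apply, so the on-study requirement falls short of the entry requirement.

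**Men.** Section 7 says 90 days and exclusion 25 says 100 by regimen. Section 9.3.12.3.2, taken literally, gives the longer of 180 and 90, which is 180, for fathering a child and for sperm donation. On that reading men remain restricted through days 91 to 100. If its labels are a slip and the 90 was meant for monotherapy, it agrees with Section 7, and the 10-day gap to exclusion 25 returns for contraception. Exclusion 25 sets no sperm-donation period, so there is no 90-versus-100 conflict on that item.

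**The case against.** The strongest reply is that the two rules do different jobs. Exclusion 25 is tested at screening and concerns willingness or current use. Section 7 is the rule applied on study. They also differ in scope and method: exclusion 25 covers everyone of reproductive potential and asks for an effective method, whereas Section 7 covers patients sexually active with a relevant partner and prescribes particular methods. A patient who keeps to the longest stated period complies with everything, so the rules are mismatched rather than incompatible. For women, Section 7 also ends only the mandated minimum and directs a conversation with a physician before stopping.

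Most of this stands, and it keeps the point minor. It does not remove the point: both texts fix how long the same kind of commitment lasts after the same dose, and no instruction tells a site to apply the longer period.

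A reader might infer three stronger things that the documents do not support:

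- That every cohort 1 patient, men included, has a 10-day shortfall that extends to sperm donation. Section 9.3.12.3.2 read literally, and the silence of exclusion 25 on sperm donation, rule that out.
- That the gap is 10 days on any reading. It is 10 only if exclusion 25 is read by regimen.
- That 90 days is unsafe. No evidence on that is given in either direction.

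**Conclusion.** The inconsistency is real and minor. For durvalumab monotherapy, Section 7 mandates 90 days and exclusion 25 requires 100, with no rule of precedence. The gap is 10 days on the by-regimen reading, which is the more natural one, and 90 days on the literal reading. It is a clear shortfall for women and a set of conflicting periods for men. It is an error of consistency, not a design choice, and it touches no endpoint, stopping rule or analysis.

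Two things cannot be settled from the documents. Section 12.1 plans to accrue 20 patients to each cohort, but the number of reproductive potential is not given. The consent form is not among the pages available, so the duration told to participants is unknown here.

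**What to change.** Four wording changes or checks:

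1. In Section 7, change the monotherapy period for women and for men from 90 to 100 days, to match what exclusion 25 already demands at entry.
2. In exclusion 25, replace the longer-of clause with wording by regimen: 180 days after the combination, 100 days after monotherapy.
3. In both sentences of Section 9.3.12.3.2, label the periods as durvalumab plus tremelimumab (180 days) and durvalumab monotherapy (100 days), so that partner-pregnancy follow-up matches the restriction.
4. Check that the consent form states the same periods.

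The cost is an amendment to three sections and at most 10 more days of contraception under Section 7 for cohort 1 patients of reproductive potential. The third change also shortens the literal 180-day period for cohort 1 men, and the partner-pregnancy follow-up, by 180 − 100 = 80 days. The sponsor should confirm that the 180-day label on monotherapy was unintended before making it.
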